8.2 Responsibility for Analyses/In-house Blinding

The statistical analysis of the data obtained from this trial will be the responsibility of the Clinical Biostatistics department of the Sponsor.

This trial will be conducted as a double-blind trial under in-house blinding procedures. The official final database will not be unblinded until medical/scientific review has been performed, protocol violators have been identified, and data have been declared final and complete.

The Clinical Biostatistics department will generate the randomized allocation schedule(s) for trial treatment assignment.

8.3 Hypotheses/Estimation

Objectives and hypotheses of the trial are stated in Section 3.0.

8.4 Analysis Endpoints

Immunogenicity and safety endpoints that will be evaluated for between-group differences are described below.

8.4.1 Immunogenicity Endpoints

The primary endpoints for VZV immunogenicity will be the antibody response rates and GMTs after the first dose of VARIVAXTM in subjects who were initially seronegative to VZV at baseline.

The response rate and GMT endpoints and the criteria for baseline seronegativity are defined below:

- The response rate is the percentage of subjects with VZV antibody titer ≥5 gpELISA units/mL 6 weeks Postvaccination 1 among subjects who were seronegative to VZV (titer <1.25 gpELISA units/mL) at baseline.
- The postvaccination antibody GMTs 6 weeks Postvaccination 1.

In addition, the VZV seroconversion rate (defined as the proportion of subjects with baseline VZV titer <1.25 gpELISA units/mL and with postvaccination VZV titer \geq 1.25 gpELISA units/mL) will be summarized after the first dose. For subjects who are initially seropositive (baseline VZV antibody titer \geq 1.25 gpELISA units/mL), the geometric mean fold rise (GMFR) and the percentage of subjects achieving \geq 4-fold rise in antibody titer from baseline will be summarized after the first dose.

8.4.2 Safety Endpoints

Refer to Section 4.2.3.2 for the description of the safety measures in this trial.

The key safety endpoints evaluated as Tier 1 events are as follows: the rate of elevated temperature from Days 1 to 42 after each vaccination; varicella-, zoster-, measles-, or rubella-like rashes or mumps-like symptoms, and all injection-site rashes occurring within Days 1 to 42 after each vaccination, and all solicited injection-site reactions (redness, swelling, pain/tenderness) occurring within Days 1 to 5 after each vaccination.

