4.2.3.2 Safety Endpoints

Throughout the clinical development program VARIVAX[™] has demonstrated an acceptable safety profile in children. Moreover, across dose ranges and manufacturing processes, aggregate safety data from the varicella clinical development program demonstrate the consistency of the safety profile of VARIVAXTM, with similar rates of local and systemic adverse experiences and temperature data. Additionally, in clinical studies that have evaluated the concomitant administration of VARIVAXTM with M-M-RTM II, concomitant use did not adversely affect the safety profile of either vaccine.

In clinical studies using a 2-dose regimen of VZV-containing vaccine in children, the incidence of injection-site reactions after vaccination was generally higher Postvaccination 2 than Postvaccination 1, although the injection-site reactions were short in duration and mild in intensity and size; whereas, significantly lower incidences of elevated temperatures and noninjection-site varicella-like rashes were observed Postvaccination 2 compared with Postvaccination 1.

As with previous VARIVAX[™] studies, the postvaccination safety follow-up period will be 42 days after each vaccination. The safety parameters for this trial will include the proportion of subjects with the following:

- 1) elevated temperatures $\geq 102.2^{\circ}$ F [$\geq 39.0^{\circ}$ C] oral equivalent) up to 42 days after each trial vaccination;
- 2) varicella-like, zoster-like, measles-like, or rubella-like rashes or mumps-like symptoms occurring up to 42 days after each trial vaccination;
- 3) solicited injection-site reactions (using the electronic vaccination report card [eVRC]), such as redness, swelling, and pain/tenderness/soreness, occurring within 5 days after each trial vaccination;

- 4) all unsolicited injection-site reactions occurring on Days 1 through 42 after each trial vaccination;
- 5) systemic adverse experiences up to 42 days after each trial vaccination;
- 6) serious adverse experiences throughout the trial duration; and
- 7) medically attended adverse events from Day 133 through Day 271.

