Statistical Methods for Key Safety Analyses	The analysis of safety results will follow a tiered approach. The tiers differ with respect to the analyses that will be performed.
	Tier 1 safety endpoints include the rate of fever (temperature $\geq 102.2^{\circ}$ F [$\geq 39.0^{\circ}$ C] oral equivalent) from Days 1 to 42 after each vaccination; varicella-, zoster-, measles-, or rubella-like rashes or mumps-like symptoms, and injection-site rashes occurring within Days 1 to 42 after each vaccination; and solicited injection-site reactions (redness, swelling, pain/tenderness) within Days 1 to 5 after each vaccination. For Tier 1 events, inferential testing for statistical significance with p values and 95% CIs will be provided for between-group comparisons.
	Any adverse experiences (specific terms as well as system organ class [SOC] terms) that are not pre-specified as endpoints of particular interest will be classified as belonging to Tier 2 or Tier 3. Tier 2 parameters will be assessed via point estimates with 95% CIs provided for between-group comparisons; only point estimates by vaccination group are provided for Tier 3 safety parameters. Analyses will be performed using the Miettinen and Nurminen method [17].
Interim Analyses	No interim analyses are planned for this trial.
Multiplicity	No multiplicity adjustment is planned as success of the trial requires success on both the noninferiority and acceptability hypotheses.
Sample Size and Power	The planned sample size is ~600 subjects in total (~300 in each group). Assuming 80% evaluability, 90% Postvaccination 1 response rates, and a standard deviation of 1.2 for the log-transformed Postvaccination 1 antibody titers, this trial has 94.1% power for demonstrating noninferiority of the response rate, 95.8% power for demonstrating acceptability of the GMT, and >99.9% power for demonstrating acceptability of the response rate at an overall 2-sided 5% α -level. The overall power for the primary immunogenicity hypotheses is estimated to be 90% (= 0.941 × 0.958 × >0.999).

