8.6.2 Statistical Methods for Safety Analysis

Safety and tolerability will be assessed by clinical review of all safety data collected throughout the trial.

The analysis of safety results will follow a tiered approach (Table 4). The tiers differ with respect to the analyses that will be performed. Safety parameters or adverse experiences of particular interest that are identified a priori constitute "Tier 1" safety endpoints that will be subject to inferential testing for statistical significance with p values and 95% CIs provided for between-group comparisons. Other safety parameters will be considered Tier 2 or Tier 3. Tier 2 parameters will be assessed via point estimates with 95% CIs provided for between-group comparisons; only point estimates by vaccination group are provided for Tier 3 safety parameters.

Any adverse experiences (specific terms as well as system organ class [SOC] terms) that are not pre-specified as endpoints of particular interest will be classified as belonging to Tier 2 or Tier 3, based on the number of events observed. Membership in Tier 2 requires that at least 4 subjects in any vaccination group exhibit the event; all other adverse experiences will belong to Tier 3.

The threshold of at least 4 events was chosen because the 95% CI for the between-group difference in percent incidence will always include zero when treatment groups of equal size each have less than 4 events and, thus, would add little to the interpretation of potentially meaningful differences. Because many 95% CIs may be provided without adjustment for multiplicity, the CIs should be regarded as a helpful descriptive measure to be used in review, not a formal method for assessing the statistical significance of the between-group differences in adverse experiences and predefined limits of change.

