For this protocol, the following are considered Tier 1 events: elevated temperatures (maximum reported temperature $\geq 102.2^{\circ}$ F [$\geq 39.0^{\circ}$ C] oral equivalent) within Days 1 to 42 after each vaccination; vaccine-specific measles-, rubella-, varicella-, zoster-like rashes, mumps-like symptoms, and injection-site rashes occurring within Days 1 to 42 after each vaccination; and solicited injection-site reactions (redness, swelling, pain/tenderness) within Days 1 to 5 after each vaccination. In addition, the broad clinical categories consisting of the percentage of subjects with any adverse experience, a vaccine-related adverse experience, a serious adverse experience, an adverse experience that is both vaccine-related and serious, and who discontinued due to an adverse experience will be considered Tier 2 endpoints. The *p* values (Tier 1 only) and 95% CIs (Tier 1 and Tier 2) will be provided for between-group differences in the percentage of subjects with events; these analyses will be performed using the Miettinen and Nurminen method, an unconditional, asymptotic method [17].

Extended Safety Follow-up Period (Day 133 [+14 days] to Day 271 [+14 days])

For the extended safety follow-up period, a summary will be provided of the number of subjects in each vaccination group who report a serious adverse experience or a medically attended adverse experience. For this extended safety follow-up period, these events will be treated as Tier 2 events, with 95% CIs being presented for the between-group risk differences in the percentage of subjects reporting these events. For serious adverse experiences, a

summary along with a between-group comparison will also be provided for the entire trial (i.e., from enrollment through 180 days Postvaccination 2).

Because many 95% CIs may be provided without adjustment for multiplicity, the CIs should be regarded as a helpful descriptive measure to be used in review, not a formal method for assessing the statistical significance of the between-group differences in adverse experiences.

Safety Tier	Safety Endpoint [†]	p Value	95% CI for Treatment Comparison	Descriptive Statistics
	Rate of elevated temperatures (≥ 102.2°F [39.0°C]) [‡] from Days 1 to 42 postvaccination	Х	X	Х
Tier 1	Vaccine-specific systemic rashes (measles-like, rubella-like, varicella- like, zoster-like), mumps-like symptoms, and injection-site rashes Days 1 to 42 postvaccination	Х	X	Х

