	Injection-site reactions (redness, swelling, and pain/tenderness) Days 1 to 5 postvaccination	Х	X	Х
	Any AE Days 1 to 42 postvaccination		Х	Х
	Any serious AE Days 1 to 42 postvaccination		X	Х
	Any vaccine-related [§] AE Days 1 to 42 postvaccination		X	Х
	Any serious and vaccine-related [§] AE Days 1 to 42 postvaccination		X	Х
Tier 2	Discontinuation due to AE Days 1 to 42 postvaccination		Х	Х
	Specific systemic AEs [¶] and SOCs (incidence \geq 4 subjects in one of the vaccination groups) during Days 1 to 42 postvaccination and injection-site reactions [¶] (incidence \geq 4 subjects in one of the vaccination groups) Days 1 to 5 postvaccination and Days 1 to 42 postvaccination		x	Х

Table 4	Analysis	Strategy	for Safety	Parameters
Table 4	Analysis	Shalegy	for Safety	Farameters

Safety Tier	Safety Endpoint [†]	p Value	95% CI for Treatment Comparison	Descriptive Statistics
	Specific systemic AEs [¶] and SOCs (incidence <4 subjects in all of the vaccination groups) during Days 1 to 42 postvaccination and injection-site reactions [¶] (incidence <4 subjects in all of the vaccination groups) Days 1 to 5 and Days 1 to 42 postvaccination			Х
Tier 3	Maximum temperature summary (Brighton Collaboration Cutpoints) by day range: Days 1 to 42, Days 1 to 5, Days 6 to 13, Days 14 to 28, and Days 29 to 42 postvaccination			Х
	Distribution of maximum size (for injection-site redness and swelling Days 1 to 5 postvaccination) and distribution of maximum intensity (for all other injection-site reactions Days 1 to 5 postvaccination and all systemic AEs Days 1 to 42 postvaccination)			Х
	ience references refer to Clinical AEs.	. 1 . 1 .	1 / 1 11	
[‡] For reporting purposes, temperatures will be converted to oral equivalent by adding 1.0°F to axillary temperatures and subtracting 1.0°F from rectal temperatures.				
[§] Determined by the investigator to be related to the vaccine.				
[¶] Includes only those endpoints not pre-specified as Tier 1 or not already pre-specified as Tier-2 endpoints.				
\mathbf{V} = regults will be provided				

X = results will be provided.

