The between-group comparisons described above will be made between Group 1 and Group 2 for each postvaccination follow-up period. This will be done by performing separate comparisons between VARIVAXTM PE34 process and VARIVAXTM (2016 commercial product) vaccination groups for the 42 days after receipt of the first vaccination and for the 42 days after receipt of the second vaccination. For serious adverse experiences, a summary along with a between-group comparison will also be provided for the entire primary trial phase (i.e., the combined 42-day periods after both vaccinations).

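### Do the Tier 1 tests of injection-site reactions and rashes need to name the limb, VARIVAX or M-M-R II, that they refer to?

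*Combined protocol and SAP*

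**What the plan says.** Section 7.1.2.1.2 assigns VARIVAX to the left arm or thigh and M-M-R II to the right. Sections 7.1.1.9 and 7.1.2.1.5 solicit local reactions for both injections over Days 1 to 5.

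The analysis text on these endpoints reads as follows:

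- Section 4.2.3.2 lists solicited reactions "occurring within 5 days after each trial vaccination".
- Section 8.1 has "rubella-like rashes or mumps-like symptoms, and injection-site rashes occurring within Days 1 to 42 after each vaccination".
- Section 8.4.2 has "all solicited injection-site reactions (redness, swelling, pain/tenderness) occurring within Days 1 to 5 after each vaccination" and "and all injection-site rashes occurring within Days 1 to 42 after each vaccination".
- Table 4 has "Injection-site reactions (redness, swelling, and pain/tenderness) Days 1 to 5 postvaccination".

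Section 8.6.2 makes Tier 1 endpoints "subject to inferential testing for statistical significance with p values and 95% CIs provided for between-group comparisons". The p values and intervals concern "between-group differences in the percentage of subjects with events" and use the Miettinen and Nurminen method. Comparisons are made separately by dose, the first being "for the 42 days after receipt of the first vaccination". None of these places mentions a limb.

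**The concern.** Only the VARIVAX injection differs between the groups; M-M-R II is common to both. A subject-level endpoint that counted a reaction in either limb would include children who reacted only to M-M-R II. Those children carry no direct information on PE34 against the 2016 product, and they would tend to pull the two percentages together. In a safety comparison that is the uncomfortable direction, because a real increase in local reactions becomes harder to see. If instead each limb were tested, the unadjusted p values for these endpoints would double. On either view, two analysts working from the same text could produce different Tier 1 tables.

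**Working it through.** **1. Does the text settle the site?**

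| Place | What it suggests |
|---|---|
| Section 3.2, secondary safety objective | Concerns the two doses of PE34, so leans to the VARIVAX site |
| Sections 7.1.1.9 and 7.1.2.1.5 | Use *trial vaccine* for the VARIVAX products and name M-M-R II separately, so lean to VARIVAX |
| Section 5.2 Table 1 and Section 7.1.2.1.2 | Include M-M-R II among the trial vaccinations, so lean the other way |
| Section 8.4.2, the word *all* | May mean all reaction types, each site in turn, or any site; absent before these terms in Section 8.1, Section 8.6.2 and Table 4 |
| Section 8.6.2, percentage of subjects | Fixes the unit of analysis only; fits a VARIVAX-site count, one row per site, or an any-site count |

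The site is therefore not stated. Equally, nothing instructs the analyst to pool the limbs.

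**2. The plan's own figures.** Inputs from Section 8.9.2: 300 per group after dose 1, 285 after dose 2, two-sided 0.05. With the pooled-variance normal approximation,

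power = Φ{[d − 1.96·√(2p̄(1−p̄)/n)] / √([p₁(1−p₁)+p₂(1−p₂)]/n)}.

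For 20% against 29.9%, n = 300: d = 0.099 and p̄ = 0.2495. The standard error is 0.0353 under the null and 0.0351 under the alternative. Then (0.099 − 0.0693)/0.0351 ≈ 0.85, giving power 0.802. All seven rows of Table 5 give 79.4% to 80.2%, and all seven of Table 6 give 79.6% to 80.4%. Both tables reproduce. They are generic tables of hypothetical rates and promise nothing about a particular injection site.

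**3. What an either-limb count could do.** *Assumptions not in the documents:* the Table 5 row is read as VARIVAX-site rates p, and the M-M-R II-site rate m is equal in both groups.

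- Independent sites: any-site rate = 1 − (1−p)(1−m), so the difference shrinks by the factor (1−m). At m = 20% the rates are 1 − 0.80×0.80 = 36.0% and 1 − 0.701×0.80 = 43.9%.
- Disjoint sites: any-site rate = p + m. The difference stays at 9.9 points but the variance changes.
- Nested (every M-M-R II reactor also reacts at the VARIVAX site): any-site rate = p.

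Power by exact enumeration of the Miettinen–Nurminen test, n = 300 per group, against 0.803 at the VARIVAX site alone:

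| m | Independent | Disjoint | Nested |
|---|---|---|---|
| 5% | 0.723 | 0.756 | 0.803 |
| 10% | 0.646 | 0.723 | 0.803 |
| 20% | 0.510 | 0.694 | 0.803 |
| 30% | 0.399 | 0.693 | not possible (m exceeds the 20% control rate) |

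With between-site correlation of 0.3 to 0.5 and m = 20%, power is 43% to 47%. At the other extreme, if m = 30% and overlap is complete in the opposite direction, any-site rates are max(20%, 30%) = 30% and max(29.9%, 30%) = 30%, and the contrast vanishes. The result therefore runs from no loss to total loss, according to inputs the documents do not give.

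**4. What by-site reporting does.** One row per limb leaves the VARIVAX-site comparison at 0.803. Testing both limbs gives 4 endpoints (redness, swelling, pain, rash) × 2 doses × 2 sites = 16 unadjusted p values instead of 8. The plan already makes no multiplicity adjustment for safety.

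**The case for a change.** The best case for acting is that these are among the few safety endpoints chosen in advance for inferential testing, and a p value whose event is not fully defined is not fully prespecified. The blinding rules in Section 8.2, and the provision in Section 8.0 for a supplemental plan, limit when the choice can be made but do not make it. One sentence would close the gap. It is also fair that Section 7.1.2.1.2 requires only the location of each injection to be recorded. Whether the limb of each reaction is captured depends on the eVRC and eCRF, which are not in the documents.

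The wording gap stands. Its consequence does not. The loss arises only under one reading, which the plan does not direct, and its size rests wholly on assumed rates and dependence. Testing the VARIVAX site alone is a reasonable preference, but an any-site endpoint is also legitimate for a vaccine studied as given together with M-M-R II. The plan is not wrong for leaving either open.

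**Conclusion.** No change to the plan is called for. The site is unstated, but this is a gap that analysts can fill sensibly. Reactions are solicited for two injections in separate limbs, the safety objective concerns PE34, and reporting by site is consistent with every relevant section and yields a sound comparison. Safety is a secondary objective with no hypothesis or success criterion, and Section 8.6.2 rests its assessment on clinical review of the safety data. The three primary immunogenicity hypotheses are untouched, and Tables 5 and 6 are correct as they stand.

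The fall in power from 80% to as little as 40% with independent sites is an illustration conditional on an either-limb count and on M-M-R II rates that the documents do not contain. It is not an estimate for this trial. The conclusion assumes that the limb of each reaction is captured, which the available documents neither confirm nor contradict.

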8.5 Analysis Populations

8.5.1 Immunogenicity Analysis Populations

8.5.1.1 Per-protocol Population

The primary immunogenicity analyses will be based on the PP population. The PP population consists of those subjects who are not considered as protocol violators. Violations include but are not limited to: failure to receive the full, scheduled doses (at least

46

90 days between doses 1 and 2) of correct clinical material and lack of valid serology results available from 27 to 84 days following the first dose. The day range for inclusion of postvaccination blood samples in the statistical analysis is wider than the visit window provided earlier in this protocol (+ 14 days for the 6-week serology testing), but is being used to be consistent with other studies evaluating VZV-containing vaccines.

In addition to meeting the PP population requirements, the primary analysis requires specific baseline criteria be met for VZV: baseline VZV antibody titer <1.25 gpELISA units/mL. Additional immunogenicity summaries will be made for subjects who meet the PP population requirements but do not meet the baseline antibody requirement for VZV (e.g., a summary of Postvaccination 1 VZV immunogenicity in otherwise PP subjects who have a baseline VZV antibody titer \geq 1.25 gpELISA units/mL; see Section 8.6.1.4 for details).

Supportive summaries at Postvaccination 1 will also be made for the PP population, as described in Section 8.6.1.4.

The final determination on protocol violations, and thereby the composition of the PP population, will be made before unblinding of the database and will be documented in a separate memo.

8.5.1.2 Full Analysis Set

A supportive summary and analysis for VZV immunogenicity will be based on the FAS. The FAS population consists of all randomized subjects with a valid serology measurement, regardless of protocol violations. Subjects will be included in the vaccination group to which they are randomized for the FAS population. As a supportive analysis, the primary immunogenicity hypotheses will be evaluated on the FAS population in subjects meeting the VZV baseline antibody requirement to assess the robustness of the primary conclusions based on the PP population.

8.5.2 Safety Analysis Population

The ASaT population will be used for the analysis of safety data in this trial. The ASaT population consists of all randomized/allocated subjects who received at least 1 dose of trial Subjects will be included in the treatment group corresponding to the trial treatment. treatment they actually received for the analysis of safety data using the ASaT population. For most subjects this will be the treatment group to which they are randomized. Subjects who take incorrect trial treatment for the entire treatment period will be included in the treatment group corresponding to the trial treatment actually received (e.g., a subject who was randomized to Group 1 but received all vaccines according to the Group 2 schedule will be summarized with Group 2 subjects). Subjects who receive a mixed regimen (e.g., received VARIVAX[™] PE34 process at Visit 1, but received VARIVAX[™] [2016] commercial product] at Visit 3) will have their Postvaccination 1 safety data summarized with the group corresponding to the vaccine(s) received (for this example, with Group 1 subjects), and subsequent safety data summarized separately from the Postvaccination 2 summary for Group 1 and Group 2 subjects.

